Aim 1: To identify the key physiological parameters of swallowing which are associated with impaired swallowing safety (i.e., penetration-aspiration) and efficiency (i.e., post-swallow residue). To address this research aim, we will collect x-ray videos of swallowing (known as videofluoroscopy). We will then perform blinded quantitative analysis of swallowing kinematics and events, following a series of standard operating procedures developed in the [name] Swallowing Lab. This procedure will yield measures of swallowing physiology, which we can link to measures of swallowing safety and efficiency. We will also collect a series of measures regarding non-swallowing factors (e.g., oral-motor strength/function, liquid sip size) which may influence the analysis results. *Significance:* This analysis will reveal the most clinically relevant parameters for dysphagia assessment, and highlight the specific physiological mechanisms which predict or contribute to impairments in swallowing safety and efficiency.

Aim 2: To explore how factors related to liquid thickness impact swallowing physiology and function. Throughout the videofluoroscopy, participants will swallow sips of liquids ranging in thickness (from thin to extremely thick). The liquids will be mixed with a contrast agent (barium sulfate) so they are visible on x-ray. Liquid thickness will be explored in terms of its influence on swallowing safety and efficiency, and as a covariate upon swallowing physiology. *Significance:* This research aim will provide insight into the efficacy of thickened liquids to reduce instances of aspiration in individuals with neurodegenerative

diseases, and will allow us to determine what constitutes an optimal level of thickness for therapeutic intervention.

6. Research Plan

Protocol Review

The parent grant of which this project is a subproject has undergone scientific review by the MFSR Study Section of the National Institutes of Health (USA). The current protocol will be reviewed by the IRB at the University of Florida, where participant recruitment and data collection will take place, as well as the REB at the University Health Network, where data analysis will take place.

Funding

All costs for this study will be covered by the grant received from the National Institutes of Health (National Institute on Deafness and Other Communication Disorders, USA, Grant #: 5 R01 DC011020-05).

Participants

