With the participant seated comfortably, a small air-filled disposable bulb will be placed in the mouth, behind the front teeth, and the participant will be instructed to press as hard as they can with the front and back of the tongue, three times in each position, with 30 seconds of rest between each trial. Next, participants will be asked to swallow their saliva with the bulb at the front of their tongue, three times, with 60 seconds between each swallow. Measures will be recorded on the Tongue Strength Measurement form.

Videofluoroscopy (30 minutes):

A videofluoroscopy (i.e., swallowing x-ray) will be conducted by a speech-language pathologist and a radiology technician, at the Swallow Systems Core laboratory in Gainesville, Florida. [name] and the co-director of the Swallowing Systems Core lab own a C-Arm fluoroscopy unit that is housed in their secure research space. This C-Arm will be used to conduct all swallowing studies. This procedure will take approximately 30 minutes of the participant's time (including set-up, instructions) and will include up to 21 liquid bolus trials.

An array of barium stimuli has been developed for this study. These stimuli include thin, slightly-thick, mildly-thick, moderately- and extremely-thick liquids, defined by the International Dysphagia Diet Standardisation Initiative (IDDSI) framework. The barium stimuli used for videofluoroscopy will be prepared using E-Z-Paque® barium in 20% w/v barium concentration with starch and gum-based thickening agents (Nestlé Resource® ThickenUp® and ThickenUp Clear®). All stimuli will be prepared at the Swallowing Systems Core Laboratory, within 3 hours of the scheduled videofluoroscopy, according to a strict standard operating procedure. Following preparation, stimuli will be stored in the lab until needed.

Boluses will be presented in the following order:

- a) Three (3) swallows of Level 0 thin liquid (Bracco E-Z-Paque powdered barium, prepared in a 20% weight-to-volume concentration);
- b) Six (6) swallows of Level 1 slightly thick liquid (20% weight-to-volume barium concentration):
 - Three (3) boluses thickened with a xanthan-gum thickener (Nestlé Thicken Up Clear),
 - Three (3) boluses thickened with a starch thickener (Nestlé Thicken Up);
- c) Three (3) swallows of Level 2 thick liquid (20% weight-to-volume barium concentration, thickened with a xanthan-gum thickener (Nestlé Thicken Up Clear);

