Throughout the study, steps will be taken to ensure participant safety and minimize risk of adverse events. We anticipate that comprehensive examinations of the full continuum of liquid consistencies may not be possible for all patients in this study, and we will adhere to strict rules to terminate the protocol, if necessary. If aspiration or penetration leaving residue in the laryngeal vestibule is observed on two trials of the same stimulus, the remaining trial(s) of that stimulus will be skipped and the examiner will move on to the next IDDSI level. If a participant displays 3 instances of aspiration (PAS ≥ 6), the swallowing x-ray will be stopped and data collection will discontinue for that participant. The protocol will be terminated after 3 observations of penetration-aspiration. If severe levels of pharyngeal residue are observed in an individual (i.e., either the valleculae or pyriform sinuses are judged to be 75% full or more, with risk of overflowing) and persist despite compensatory maneuvers, the swallowing x-ray will be terminated and the participant's dysphagia will be managed according to best practice standards of care.

After the initial swallow of each bolus is collected for research purposes, the attending speech-language pathologist may instruct the patient to perform additional tasks (such as coughing) or clearing swallows using compensatory maneuvers (e.g. chin down position) to manage instances of aspiration or residue, as deemed clinically necessary. These subsequent swallows using compensatory maneuvers will be noted on the appropriate Videofluoroscopy Clinical Reporting Form and will not be included in the data analysis. The attending clinician may terminate the protocol at any time if he or she deems the patient to be at significant risk for adverse events.

In the event of an unanticipated adverse response, the participant's neurologist will be immediately notified and the patient will be seen for a complete evaluation. Data, adverse events, and individual subject safety are monitored throughout each subject's evaluation as well as during weekly laboratory meetings with the PI and study team.

Data Processing and Analysis

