All data processing will take place at the University Health Network, Toronto Rehabilitation Institute. Full-length videofluoroscopies will be transferred from the University of Florida to the Swallowing Rehabilitation Research Lab at the Toronto Rehabilitation Institute through a secure file transfer protocol.

An engineer from [name] research team will segment each videofluoroscopy into individual bolus clips (i.e., one video clip, per bolus). Bolus-level videos will be de-identified to the highest possible degree and randomized for blinded analysis. Videofluoroscopy rating will follow a standard operating procedure, developed in the Swallowing Rehabilitation Research Lab. A minimum of twenty-five percent (25%) of the videos will be rated in duplicate to obtain measures of inter- and intra-rater agreement.

Planned Statistical Analysis

Once the videofluoroscopy ratings have been completed, statistical analysis will be completed either in [name] laboratory or in [name] laboratory. Transfer of anonymized excel data sheets containing the information needed for these analyses will be covered by a data transfer and sharing agreement.

Statistical analysis will be conducted in a stepwise fashion, to address the research questions and identify trends within the data. We will begin by exploring correlations between measures of interest, to identify and appropriately address potential non-independence and collinearity. If two or more measures are found to be highly correlated with one another, we will retain the measure(s) which show the least variability and remove the remaining measures from the analysis. Further, because we are obtaining multiple bolus trials from the same participants, we will also calculate within-subject variance for each parameter of swallowing physiology and function.

We will explore how parameters of swallowing physiology vary based on swallowing function status (i.e., swallowing safety or efficiency) through a series of repeated measures ANOVAs, Spearman's Rho and Pearson's correlation coefficients, and logistic regression (statistical tests will be defined by the type of data). Following this, we will explore how liquid thickness modulates the relationships between parameters of swallowing physiology and function, as a covariate, using a path analysis.

Privacy and Confidentiality

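### Physiology is compared by observed safety or efficiency status with repeated measures ANOVA, but the level of status is undefined: either reading can lose participants, and each answers a different question

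*Combined protocol and SAP*

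**What the plan says.** Aim 1 (section 5) is worded as follows: "To identify the key physiological parameters of swallowing which are associated with impaired swallowing safety", with efficiency added alongside safety. The analysis for it, in Planned Statistical Analysis (section 6), will explore how physiological parameters "vary based on swallowing function status (i.e., swallowing safety or efficiency) through a series of repeated measures ANOVAs". The same sentence adds "Spearman's Rho and Pearson's correlation coefficients, and logistic regression (statistical tests will be defined by the type of data").

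On clustering, the plan states: "because we are obtaining multiple bolus trials from the same participants, we will also calculate within-subject variance for each parameter". No model is said to use that variance, and no mixed model, GEE or participant effect is named.

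The examination (section 6, Videofluoroscopy) "will include up to 21 liquid bolus trials": seven stimuli of three boluses each, listed from thin to extremely thick. Safety Precautions makes the number of boluses depend on the outcome:

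- After two events on one stimulus, "the remaining trial(s) of that stimulus will be skipped and the examiner will move on to the next IDDSI level".
- After three instances of aspiration, defined there as PAS of 6 or more, "the swallowing x-ray will be stopped and data collection will discontinue for that participant".
- The next sentence gives a differently defined trigger, three observations of penetration-aspiration.
- A separate rule covers severe residue that persists.

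**The concern.** Status is an outcome observed during the examination, not a condition assigned by design. Nothing guarantees that each participant supplies both states, or the same number of boluses in each. Classical repeated measures ANOVA needs every participant to fill every cell, so the unstated level of status decides who stays in the analysis.

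It also decides the question. Whether people who aspirate swallow differently from those who do not is a between-person question. Whether the same person swallows differently on an unsafe bolus is a within-person question. Aim 1 could mean either or both, and a parameter may matter for one and not the other. If the choice is left until the data are in hand, the set of parameters called key may reflect that choice.

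**Working it through.** **1. The plan's own figure.** Section 6 gives 36 participants for d = 0.5, 80% power and alpha 0.05 (two-sided assumed), without naming the test.

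- Paired t-test (noncentral t, noncentrality d√n): n = 34, power 81%. At 36 the power is 83%, and at 40 it is 87%.
- Signed-rank test: 34 / 0.955 = 35.6, so 36.
- Two independent groups, normal approximation: 2 × (1.96 + 0.84)² / 0.5² = 62.8, so 63 per group.

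The 36 therefore fits a within-person contrast to which everyone contributes. It was set for bolus flow measures, not for the status contrast, so it is context only.

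**2. Two readings of a complete-case ANOVA.**

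| | Status repeated (per bolus) | Status as group, liquid repeated |
|---|---|---|
| Who is lost | Always-safe and always-unsafe participants | Those with missing liquid cells after a stop, or missing bolus cells after a skip |
| Question answered | Within person only | Mainly between people |

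**3. Size of the losses, safety status only.** The documents give no event rates, so these are assumptions: 40 participants, 21 boluses in listed order, each participant's risk drawn on the logit scale, no thickness effect, the remaining trials of a stimulus skipped after two events, and the examination stopped after three.

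| Mean logit | Both states, SD 2 | Both states, SD 1 | Stopped early, SD 2 |
|---|---|---|---|
| -4 | 16.5 | about 15 | 6.9 |
| -3 | 22.6 | 24.8 | 12.6 |
| -2 | 27.0 | 33.1 | 19.8 |

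With status repeated, 40 - 33 = 7 to 40 - 15 = 25 participants are lost. With liquid repeated, the count missing at least one of the seven stimuli is about 6 to 18 at SD 2 and as low as about 1 at SD 1.

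A different assumption, beta-distributed risk with mean 5 to 30% and intraclass correlation 0.2 to 0.6, gives about 5 to 34 participants with both states. For a residue-type status at 30 to 50% with no stopping, it gives 22 to 39.

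If d = 0.5 is applied to the participants left with both states, paired power is 75% with 30, 65% with 24, 57% with 20 and 35% with 12.

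**4. Does the level change the answer?** A simulation took 40 × 21 boluses without stopping. The log-odds of an impaired bolus were -1.8 + 1.5u. Physiology was 0.7u plus participant noise (SD 0.5) and bolus noise (SD 1), with no effect of status within a person.

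| Contrast | Mean difference | Rejected |
|---|---|---|
| Boluses pooled, clustering ignored | 0.77 | 99.6% |
| Participants, ever against never impaired | 1.03 | 83% |
| Within person, both states (about 33 of 40) | 0.00 | 4.4% |

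The last row is correct, since there is nothing within person to find. The contrasts answer different questions, and the plan does not say which it asks.

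**5. Is thickness needed in the replacement model?** With assumed thickness effects and no status association, the split-status model without thickness falsely rejected 19% (between-person) and 8% (within-person). With thickness level added, these fell to 3% and 6%. Power for a true between-person association of 0.6 rose from 44% to 81%.

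**The case against.** A reader might infer that the plan makes status a within-person factor, so that one-state participants are certain to be dropped and the two kinds of association are mixed as well. The documents do not support that. The plan never names the repeated factor and never mentions complete-case deletion. Under the group reading, nobody is lost for lacking a state. Nor can a single ANOVA do both harms: a complete-pair within-person contrast discards between-person information and does not mix it in.

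A reader might also infer that the within-person test lacks power because it rejects only about 5% of the time for a purely between-person parameter. That is the correct type I error for the question it asks.

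The same sentence of the plan also lists Spearman correlation and logistic regression, to which one-state participants can contribute. So it is not shown that the plan as a whole would miss a between-person parameter. Step 3 rests on assumed rates, covers safety only and omits a thickness effect that Aim 2 exists to study. The analysis is exploratory.

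All of this stands as a limit on the claim. What remains is that the level of status, the handling of missing cells and the between/within split are unstated. Choosing tests by data type settles none of them, because data type does not determine the unit of comparison.

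**Conclusion.** The concern holds as a conditional one. Repeated measures ANOVA suits an observed, unbalanced status poorly when the examination is shortened because of that same outcome. If it is run on complete cases, one reading loses participants with only one state and the other loses those stopped or skipped, who are the most impaired. Under the assumed safety risks, about 15 to 33 of 40 show both states and about 1 to 18 miss at least one stimulus. These are illustrations, not forecasts, and they do not carry over to residue status. The change is worth making before analysis. It does not call into question the data to be collected or the exploratory purpose.

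**What to change.** Replace the ANOVAs by status with one bolus-level linear mixed model per physiological parameter, using all observed boluses of all participants. Include:

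- a random participant intercept;
- liquid thickness level as a fixed effect;
- status, defined per bolus, as two terms: the participant's share of impaired boluses and the bolus's deviation from that share.

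Report the two status coefficients separately, as the between-person and within-person answers. Say which of them Aim 1 relies on, or that it relies on both.

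Reconcile the two stopping triggers in Safety Precautions, since they change how many boluses are observed.

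The cost is analysis wording and modest programming, with no new data and no added burden on participants. There are three downsides. Each parameter has two coefficients to report. One-state participants still add nothing to the within-person coefficient, although they now inform the between-person one. The impaired share is imprecise for participants stopped early, because it rests on few and mostly thinner boluses.

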Videofluoroscopy (i.e., dynamic swallow x-ray) is widely considered to be the “gold standard” method for determining the nature, severity and functional consequences of abnormal swallowing physiology. Although observations from videofluoroscopy are frequently described in research literature, few studies have used objective measures to quantify the impairments and pathophysiological changes in swallowing. This makes it difficult to compare results directly across research studies, determine at what point physiological changes contribute to functional impairments in swallowing, and explore what factors lead to changes in swallowing physiology. Changes in liquid thickness, for example, have been shown to influence swallowing physiology in a predictable manner in healthy individuals and patients post-stroke; however we do not know how changes in liquid thickness modulate swallowing physiology in individuals with neurodegenerative diseases.

The purpose of this study is to conduct quantitative analysis of swallowing physiology, seen on videofluoroscopy (swallow x-ray), in order to:

- 1) Identify physiological parameters contributing to swallowing impairment; and
- 2) Determine how swallowing physiology and function differs across five levels of liquid thickness: thin, slightly-thick, mildly-thick, moderately-thick and extremely-thick.

4. Background

Dysphagia (i.e., swallowing impairment) is often characterized in terms of:

- (1) Impaired safety (i.e., food and liquids entering the airway, known as aspiration), and;
- (2) Impaired efficiency (e.g., food and liquids leaving residue in the throat after the swallow).

Impaired swallowing safety is linked to pneumonia while impaired efficiency has been indicated as a risk factor for malnutrition. Further, the accumulation of residue in the throat poses an independent risk factor for subsequent aspiration events. Dysphagia is highly prevalent in individuals with neurodegenerative diseases, such as Amyotrophic Lateral Sclerosis (ALS) and Parkinson's Disease (PD). As there is currently no cure for these complex diseases, symptomatic management of dysphagia is the current standard of care.

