Research on dysphagia in neurodegenerative diseases to-date has focused primarily upon the presence of aspiration; however, there has been relatively little attention paid to the underlying physiological differences which predict or contribute to swallowing impairment. Understanding the key mechanisms behind impairment is critical for guiding clinical assessment, predicting disease progression and providing rationale for specific management options. Thickened liquids, for example, are commonly recommended to reduce the risk of aspiration; however, the accumulation of post-swallow residue has been shown to increase with liquid thickness, particularly in individuals with oropharyngeal weakness. Few studies have systematically investigated the efficacy of thickened liquids, or how changes in liquid thickness influence swallow physiology in patients with neurodegenerative diseases. Studies which have begun to explore these relationships have been limited to one or two levels of thickness at extreme ends of the continuum (e.g., thin versus pudding/paste). The purpose of the proposed cross-sectional study is to explore the pathophysiology of dysphagia through quantitative measurements of swallowing physiology. We aim to identify the key physiological parameters of swallowing which contribute to impaired swallow safety and efficiency, and to determine how swallowing physiology and function differs across five levels of liquid thickness: thin, slightly-thick, mildly-thick, moderately-thick and extremely-thick.

This protocol outlines a subproject of a larger project entitled *Physiological Flow of Liquids Used in Dysphagia Management*. The larger project (i.e., parent grant) has been reviewed and funded by the National Institutes of Health as a 5-year R01 grant awarded to the PI ([name].).

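### The Aim 1 correlations and logistic regression have no stated unit of analysis and no participant clustering, and they leave liquid thickness to a later step

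*Combined protocol and SAP*

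**What the plan says.** Under Data Processing and Analysis, an engineer will "segment each videofluoroscopy into individual bolus clips (i.e., one video clip, per bolus", and the clips are then rated. The Videofluoroscopy section allows up to 21 boluses per person, and Participants plans 40 people.

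Planned Statistical Analysis relates physiology to safety and efficiency status by repeated measures ANOVA, Spearman and Pearson "coefficients, and logistic regression (statistical tests will be defined by the type of data". It does recognise dependence. Correlations between measures are explored first "to identify and appropriately address potential non-independence and collinearity", and "because we are obtaining multiple bolus trials from the same participants, we will also calculate within-subject variance" for each parameter.

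Thickness comes in after these tests: "we will explore how liquid thickness modulates the relationships between parameters of swallowing physiology and function, as a covariate, using a path analysis". Section 5 also plans, under Aim 2, to study the influence of thickness on safety and efficiency and to use it as a covariate for physiology.

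On what thickness does, the opening purpose section states: "Changes in liquid thickness, for example, have been shown to influence swallowing physiology in a predictable manner". This refers to healthy people and stroke patients; the same section says the effect in neurodegenerative disease is unknown. Section 4 adds that "the accumulation of post-swallow residue has been shown to increase with liquid thickness" and that thickened liquids "are commonly recommended to reduce the risk of aspiration".

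**The concern.** Two separate problems arise.

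The first is clustering. Boluses from one person resemble each other. Ordinary Pearson, Spearman and logistic tests assume independent observations. The section credits the problem but gives a concrete remedy only for highly correlated measures, which is to drop some of them. That does nothing for repeated boluses. Calculating within-subject variance is descriptive unless it enters a test, and repeated measures ANOVA does not carry its error structure into the other three methods.

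The second is confounding by thickness. If thickness moves both a physiological parameter and the chance of penetration-aspiration or residue, the two will be associated across boluses even when neither affects the other. Clustering on participant does not remove this, and a later path analysis does not correct tests already reported.

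The section uses exploratory language, but section 5 expects Aim 1 to show which parameters matter most clinically and which mechanisms lead to impairment. Intervals that are too narrow, or a thickness effect read as a mechanism, would bear directly on that claim.

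**Working it through.** The plan gives no figure for this point. Its one power figure (36 participants) is close to a paired t-test at d = 0.5 (34) and does not address the Aim 1 associations.

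**Inputs from the documents.** 40 participants; boluses in the order 3 thin, 6 level 1, 3 level 2, 6 level 3, 3 level 4 (total 21); the skip and stop rules under Safety Precautions.

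**Assumed inputs.** No true association; two-sided nominal 5%; 15% events; equal ICCs of 0.1 to 0.7 in both measures. The skip rule is coded as two events on one stimulus, then on to the next IDDSI level. The stop rule is coded as the third event. The section words the stopping trigger in two ways, and the simulation counts any event.

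**1. Pooled Pearson correlation, two continuous measures.** With m boluses each, the variance factor is 1 + (m − 1) × ICCx × ICCy, and the actual error is 2 × [1 − Φ(1.96/√factor)]. For m = 21 and ICC 0.3 the factor is 1 + 20 × 0.09 = 2.8; 1.96/√2.8 = 1.171; error 24.1%.

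| ICC, both measures | Factor, m = 21 | Pearson, 21 boluses | Pearson, 6 boluses | Pearson, 3 boluses |
|---|---|---|---|---|
| 0.1 | 1.2 | 7.4% | 5.6% | 5.2% |
| 0.3 | 2.8 | 24.1% | 10.4% | 7.1% |
| 0.5 | 6.0 | 42.4% | 19.1% | 11.0% |
| 0.7 | 10.8 | 55.1% | 29.1% | 16.4% |

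If either ICC is 0, the factor is 1 and there is no inflation. Simulation with all 21 boluses agreed (8%, 24%, 43%, 56%).

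**2. Pooled logistic regression.** Under the skip and stop rules it rejects 6%, 9%, 12% and 18% at the four ICCs (1,500 runs each). At ICC 0.5 the formula above gives 42% against 12% here, so it must not be carried over. Two things separate them. Dichotomising lowers the ICC (a latent 0.5 became about 0.29 at 20% events). The rules also shorten the series in people with events: with all 21 boluses the logistic figures were 7%, 14%, 32% and 42%.

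**3. Thickness omitted, participant treated as the cluster.** Thickness raises the parameter and lowers event liability by the same amount per level, under the skip and stop rules.

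- At 0.2 SD per level (4 × 0.2 = 0.8 SD from thin to extremely thick), logistic GEE without thickness rejects 17%, 20%, 18% and 16%. Repeat runs put the range at about 16% to 25%.
- At 0.1 SD per level it rejects about 5% to 8%.
- For a residue-type outcome, where thickness raises both sides by 0.2 SD per level, it rejects 15%, 13%, 11% and 9%.
- With thickness in the model, the rate returns to 3% to 6%.

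**4. Plain participant mean over all observed boluses.** Under the skip and stop rules this rejects 10% at ICC 0.1, falling to 5% at ICC 0.7, with no thickness effect. If thickness shifts only the parameter, it rejects about 38% falling to about 13%; these figures move by a few points with how the skip rule is coded. People with events contribute fewer and thinner boluses, so their mean depends on outcome and thickness.

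**5. Recommended models, same settings.** GEE with small-sample correction, thickness and diagnosis: 3% to 6%. Linear mixed model: 4% to 6%. Logistic mixed model: 4.5% to 7%. A correlation within the thin level, adjusted for diagnosis: 4.5% to 7%. Later levels, which lose participants to the stop rule, were not assessed.

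**The case against.** The strongest reply is that the plan never says boluses will be pooled. It announces an intention to deal with non-independence, lists repeated measures ANOVA in the same sentence as the other tests, and will calculate within-subject variance. A reader might infer from the test names that 840 boluses (40 × 21) will be treated as independent. The documents do not support that inference; what they show is that no unit of analysis is given for three of the four methods. The pooled figures are therefore conditional.

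A reader might also infer that thickness is ignored. It is not: Aim 2 and the path analysis both include it. What stands is that it is absent from the first-step Aim 1 tests.

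The sizes are also open to challenge. The largest percentages apply to two continuous measures with all 21 boluses observed, not to binary safety status under the skip and stop rules. The thickness bias is clear at 0.2 SD per level but nearly disappears at 0.1 SD, and the documents do not say which is closer for this population.

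Finally, one could answer that a participant average solves everything. With complete and balanced boluses it would hold about 5%. Here the fixed thin-to-thick order and the outcome-driven loss of later boluses prevent that.

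**Conclusion.** The concern holds as a gap in method for the Aim 1 association tests, and it should be fixed. The plan names methods that need independent observations for data that are repeated within people, gives no means of handling this in those methods, and leaves out at the first step a variable that its own background links to both sides.

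Under the stated assumptions, the cost of pooling ranges from slight to severe for a correlation of continuous measures and is moderate for logistic regression under the skip and stop rules. The cost of omitting thickness ranges from negligible to roughly three to five times the nominal 5% (16% to 25%), even with clustering. Confidence in the size is medium, because no ICC, event rate or thickness effect is documented. The documents do not support saying that Aim 1 will have an error rate of 55%, that the product of the ICCs governs the logistic analysis, or that the plan overlooks clustering or thickness altogether.

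Primary diagnosis is recorded but used in no planned analysis. In the clustered model with thickness it made little difference (4% to 10% without it and 4% to 6% with it, at a 0.5 SD shift in both measures), so it is a minor point.

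**What to change.** In Planned Statistical Analysis:

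- State the unit of analysis for each Aim 1 test.
- Make participant the cluster in the association models. A mixed model with a participant random intercept and GEE with a small-sample variance correction (40 clusters) are both acceptable.
- Include IDDSI level as a fixed effect at this first step. Primary diagnosis can be added.
- Do not use a plain participant mean across all boluses.
- If a correlation is kept, use one value per participant within a single thickness level. Pooling the three or six boluses of a level would still reject 7% to 16% or 10% to 29% at ICCs of 0.3 to 0.7.
- Report boluses observed per participant and per level, because the skip and stop rules make these depend on the outcome.

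The cost is a few sentences, modest extra modelling, wider intervals and up to five degrees of freedom (four for the five levels, one for diagnosis). A within-level correlation uses fewer boluses. All the variables are already collected, and no clinical procedure changes.
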